# 22.0 Provisions to Protect the Privacy Interests of Subjects

- 22.1 Privacy interests for subjects will be maintained by limiting interaction with subjects and LAR to only study personnel at the discretion of the treating physician.
- 22.2 This study is voluntary, the physicians involved do not have any financial gain or interest with the study. Subjects may withdraw participation at any time and their care and treatment at CMH will not be compromised. Subjects and their families will be told that there participation is voluntary and that they may stop at any time.
- 22.3 Only IRB approved members of the study team will be granted access to the study folder located on the network drive or the REDCap database. Additionally, study team members who are responsible for collected data only will be granted limited access to REDCap, allowing them to record data only.
- 22.4 PHI to be accessed and/or recorded for this research study includes: DOB, MRN, dates of service (US SWE exams, conditioning regimen, HSCT, lab dates and dates of severity milestones and death of applicable) will be recorded.
- 22.5 HIPAA authorization will be wrapped into permission/assent/consent form.

# 23.0 Compensation for Research-Related Injury

23.1 Regular clinical review will minimize the risk of complications or harm as a result of study participation. In the event that an adverse event results from the study procedure, it will be reviewed by the principal investigator, reported to the IRB, and dealt with per institutional policy. Treatment will be available at CMH and will be provided at the usual charge. Payment for this treatment will be the participant's responsibility as this research study does not have funds set aside to pay research participants if the research results in harm or complications. The approved IRB P/A/C will include known possible adverse events of study participation as well as payment responsibility for any adverse event.

### 24.0 Economic Burden to Subjects

24.1 There is no costs to patients for participating in this research study. Patients who agree to study participation will not be charged for the ultrasound examinations or Lumason contrast agent.

### 25.0 Permission/Assent/Consent Process

- 25.1 Indicate whether you will you be obtaining permission/assent/consent, and if so describe:
  - P/A/C will take place in clinic, radiology department of inpatient floor prior to start of conditioning regimen.
  - Subjects will be given time to review the P/A/C for consent up to the day before the start of conditioning regimen to ensure that pre-BMTT US abdominal limited, Doppler, CEUS and SWE can be performed.

### Subjects who are not yet adults (infants, children, teenagers)

One parental/LAR permission will be required for all subjects under the age of 18.

Subjects over the age of 7 will be required to provide assent for the study and will be documented on P/A/C.

### Consent at 18 years of age, when minor subjects become adults

25.2 Subjects that turn 18 years of age during the study period will be reconsented with a short form addendum for continuation in the study.

### Non-English Speaking Subjects

• P/A/C forms will be translated into Spanish and Arabic by ORI Translations program.

### 26.0 Process to Document Permission/Assent/Consent

26.1 P/A/C will be documented by CMH research policy.

### 27.0 Setting

27.1 Describe the sites or locations where your research team will conduct the research.

- Subjects will be identified by treating BMT physician and will be approached for consent in clinic, radiology department or inpatient floor.
- Research procedures will be performed at CMH Adele Hall according to site specific regulations and standards.

# 28.0 Resources Available

- 28.1 Describe the resources available to conduct the research: For example, as appropriate:
  - From our preliminary data, patients with no SOS or mild SOS have an average increase in velocity over baseline of 0.056 m/s at day +5 with (SD of 0.22 m/s). Our four patients with moderate and severe SOS who received defibrotide had an average increase in velocity over baseline of 0.25 m/s at day +5 (SD 0.185 m/s), we would need 245 patients (13 with moderate or severe SOS and 232 with no SOS or mild SOS) to have a power of 80% to detect a difference with alpha of 0.05. We perform approximately 40 HSCT transplants at CMH every year and in combination with the other sites, we anticipate an enrollment rate of >60% to appropriately recruit enough subjects to complete the study.
  - We anticipate needing two years to recruit enough subjects to appropriately power the study and an additional one year to analyze results.
  - CMH radiology department has three GE Logiq E10 ultrasound machines and 12 dedicated sonographers to perform the imaging requirements.
  - IDS pharmacy will supply the Lumason Contrast agent.
  - All participating sites will be required to obtain IRB approval at their local institution and CMH research coordinators will ensure all modifications, amendments, continuing reviews and AE/SAE's are electronically transferred to each site. Study SOP will be utilized for document transfers and documentation of receipt will be kept.

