3.3 The long-term goal of our research is to accurately identify SOS patients who would benefit from defibrotide treatment using US SWE. The overall objective of this study is to validate SWE as an early diagnostic marker for SOS. Our central hypothesis is that SWE changes will precede clinical and conventional US diagnostic criteria for SOS. Our hypothesis has been formulated on the basis of our own preliminary data. We completed the first prospective cohort trial demonstrating that US SWE provides SOS diagnosis (80% sensitivity and 67% specificity) nine days earlier than current clinical criteria (9). SWE is widely available, has no known side effects, and is easy to learn and interpret. Our study enrolled 25 high-risk BMT patients over 18 months (five with SOS and two with severe SOS). More data is needed to determine the optimal window for testing to balance between improved test characteristics and early detection of disease. We propose conducting a prospective cohort study with 80 additional patients, 12 of which will likely develop SOS (including four with severe SOS) to optimize SWE timing. This study will increase the confidence in the findings from our preliminary study and allow us to test SWE against newly published clinical criteria. The rationale for the proposed research is that, if SWE can diagnose SOS earlier than clinical criteria, then SWE can guide early initiation of SOS treatment.

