# 6.0 **Procedures Involved**

6.1 Single-site prospective cohort study to evaluate grayscale US, Doppler US, CEUS and SWE examinations in BMT patients younger than 21 years. Patients will be identified by the study team during a weekly conference that involves the study team and the Children's Mercy BMT team. All eligible patients will be approached for written informed consent by a member of the study team and if they consent, then they will be enrolled into the study prior to the start of their conditioning regimen.

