# **13.0** Local Number of Subjects

13.1 We anticipate enrolling 80 subjects.

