# 29.0 Multi-Site Research

*29.1* Study-Wide Number of Subjects: 80

29.2 Study-Wide Recruitment Methods: CMH will be the only site recruiting subjects. The University of Washington – Seattle's involvement is to provide imaging consulting. [name] will have access to our PACS system for evaluation of the imaging for analysis and image protocol validation.

- All required approvals (initial, continuing review and modifications) will be submitted to CMH IRB (IRB of record) for approval and letter of correspondence provided by CMH IRB will be sent to each site for local IRB (relying IRB) approval. Each site will be required to send documentation of local IRB approval.
- All modifications will be communicated to sites and approved (including approval by the site's IRB of record) before the modification is implemented.
- All engaged participating sites will safeguard data, including secure transmission of data, as required by local information security policies.
- All local site investigators conduct the study in accordance with applicable federal regulations and local laws.
- All non-compliance with the study protocol or applicable requirements and any unanticipated problems will be reported in accordance with local policy.
- *29.3* Describe the method for communicating to engaged participating sites:
  - All education and training to researchers and research staff will be provided by CMH and documentation of training will be recorded.
  - All reportable events must be communicated within 5 business days of notification of reportable event to CMH study staff for submission to CMH IRB (IRB of record).
  - Interim results will be communicated through virtual meetings and electronic communication as they become available.
  - The closure of a study will be communicated through electronic documentation of correspondence letter from IRB of record to participating sites for relying IRB documentation.
  - •

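### Section 28.1 attaches 80% power to 245 patients from several sites, but the study enrols 80 at one site, where power is about 32% to 87% depending on an unstated case count

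*Protocol*

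**What the plan says.** **Power.** Section 28.1 takes pilot changes in shear wave velocity at day +5: a mean of 0.056 m/s (SD 0.22) with no or mild SOS, and 0.25 m/s (SD 0.185) in four patients with moderate or severe SOS. It concludes that "we would need 245 patients (13 with moderate or severe SOS and 232 with no SOS or mild SOS") for 80% power at alpha 0.05. It names no test, sidedness or attrition allowance.

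**Accrual.** The same bullet continues: "We perform approximately 40 HSCT transplants at CMH every year and in combination with the other sites, we anticipate an enrollment rate of >60" per cent. The next bullet says: "We anticipate needing two years to recruit enough subjects to appropriately power the study".

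**Planned size.** Section 13.1: "We anticipate enrolling 80 subjects". Section 29.1: "Study-Wide Number of Subjects: 80". The summary in section 1.0 also gives 80. Section 3.3 describes "80 additional patients, 12 of which will likely develop SOS (including four with severe SOS") and does not say how many of the 12 would be moderate.

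**Sites.** Section 6.1: "Single-site prospective cohort study to evaluate grayscale US, Doppler US, CEUS and SWE examinations". Section 29.2: "CMH will be the only site recruiting subjects"; the second institution is there for imaging consulting.

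**The concern.** The protocol's only hypothesis-test power statement belongs to a study three times the planned size (245/80 = 3.1), recruited with sites that sections 6.1 and 29.2 rule out. Yet section 28.1 still says recruitment will power the study. If the velocity difference turns out not to be significant, readers will judge that result against an 80% power that the planned 80 patients were never shown to have.

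The contrast that was powered (moderate or severe SOS against everyone else) is also not the comparison in objective 2.3. That objective compares SOS patients with one another, about 12 people by section 3.3.

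**Working it through.** **Inputs (section 28.1).** Difference = 0.25 − 0.056 = 0.194 m/s. SDs are 0.185 (moderate/severe) and 0.22 (no/mild). I assume a two-sided alpha of 0.05, since sidedness is not stated, and no dropout. Because no test is named, I use three versions of the two-sample t test: a common SD of 0.22, the pooled SD, and Welch.

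**Method.** Power comes from the noncentral t distribution with noncentrality 0.194/SE.
- Equal variances: SE = s·√(1/n₁ + 1/n₂), df = n₁ + n₂ − 2.
- Welch: SE = √(0.185²/n₁ + 0.22²/n₂), Satterthwaite df.
- 95% CI half-width = t(0.975, df) × SE.

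**Step 1: the plan's own figure, 13 versus 232.**
- Common SD 0.22: SE = 0.22·√(1/13 + 1/232) = 0.0627; noncentrality 0.194/0.0627 = 3.09; power 86.9%.
- Pooled SD: power 87.4%.
- Welch: SE = 0.0533; noncentrality 3.64; df about 14; power 92.2%.

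The stated 80% is not reproduced. At about the same split, 80% power is reached with 11 versus 196 (207 patients) under equal variances, or 10 versus 178 (188 patients) under Welch. Getting from there to 245 would take an allowance of 1 − 207/245 = 15.5% to 1 − 188/245 = 23.3%, and none is stated.

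**Step 2: how many cases among 80.** Section 3.3 expects 12 SOS cases, four of them severe, so the moderate-plus-severe count lies between 4 (none moderate) and 12 (none mild). The split in section 28.1 implies 13/245 = 5.3%, and 0.053 × 80 is about 4.

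**Step 3: power and precision with 80 patients.**

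| Cases vs rest | Power, SD 0.22 | Power, pooled | Power, Welch | CI half-width in m/s (SD 0.22 / pooled / Welch) |
|---|---|---|---|---|
| 4 vs 76 | 39.7% | 40.0% | 31.9% | 0.225 / 0.223 / 0.283 |
| 6 vs 74 | 53.7% | 54.4% | 53.7% | 0.186 / 0.184 / 0.194 |
| 8 vs 72 | 64.7% | 65.8% | 69.4% | 0.163 / 0.161 / 0.158 |
| 10 vs 70 | 73.1% | 74.6% | 79.8% | 0.148 / 0.146 / 0.139 |
| 12 vs 68 | 79.4% | 81.1% | 86.5% | 0.137 / 0.134 / 0.126 |

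Worked example, 4 versus 76 with SD 0.22: SE = 0.22·√(1/4 + 1/76) = 0.1129; noncentrality 1.72; t(0.975, 78) = 1.991; half-width 1.991 × 0.1129 = 0.225 m/s, which exceeds the 0.194 m/s effect.

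Simulation with the unequal SDs (200,000 runs) gives 38% (pooled) and 34% (Welch) at 4 versus 76, and 84% and 86% at 12 versus 68. The range therefore does not depend on the noncentral t approximation.

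**Step 4: accrual.** 40 transplants a year × 2 years = 80 transplants at CMH. Enrolling 80 there means enrolling nearly all of them. If the 60% floor is applied to CMH alone (an assumption, since the protocol states it for CMH and other sites together), 0.60 × 80 = 48.

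**The case against.** **The low end may be too pessimistic.** Section 3.3 reports five SOS cases among 25 pilot patients, and section 28.1 refers to four moderate or severe cases. If both describe the same cohort, 4/5 × 12 is about 10 cases among 80, and power is 73–80%. That is a fair reading and a shortfall is not certain. But the protocol does not link the two figures, and its own 13/245 split points to 4 cases. The two ends of the range both come from the document, which is why one justified case rate has to be stated.

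**The range depends on a test the protocol does not name.** True: 32–87% is the Welch range, and the pooled test gives 40–81%. An unpooled normal approximation gives 53–90% at 80 patients and would need only about 145 patients for 80% power. It also gives 95% at 13 versus 232, so no standard version at two-sided 0.05 returns the stated 80%.

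**The attrition allowance is inferred.** This stands. Two-sided alpha of 0.025 with SD 0.22 also brings 13 versus 232 to about 80%. What is certain is only that some input behind 245 is missing.

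**The 80% is conditional on 245, and 80 is stated consistently elsewhere.** Correct, and the primary objective, the timing of SWE, is not what this calculation addresses. But section 28.1 goes on to say that the planned recruitment will power the study, and it relies on sites that do not recruit. Those contradictions hold at any case count.

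**Conclusion.** The concern holds. The protocol contradicts itself on sample size (245 against 80) and on recruiting sites (several against one), and its power claim cannot be carried over to the study as planned. With 80 patients, power for the stated contrast is 32–40% at 4 moderate or severe cases, 65–69% at 8, 73–80% at 10 and 79–87% at 12. These figures rest on the pilot difference and SDs, a two-sided alpha of 0.05, a t test and no dropout. At 10 to 12 cases the study would come close to or reach 80%; at 4 it would fall far short, with an interval half-width wider than the effect. Separately, 245 does not follow from its stated inputs, and 80 patients in two years at CMH leaves almost no room for non-enrolment.

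**What to change.** 1. Decide on 80 or 245 and on the recruiting sites, and make sections 1.0, 3.3, 6.1, 13.1, 28.1, 29.1 and 29.2 agree. Restate expected accrual for the sites that remain.
2. If 80 at CMH stands, replace the 245-patient sentence with power and 95% CI half-width at 80 across 4 to 12 moderate or severe cases. Name the test, sidedness, any attrition allowance and one justified case rate. Possible wording: *With 80 patients, a two-sided pooled-SD t test at 0.05 and a difference of 0.194 m/s, power is about 40% with 4 moderate or severe cases (95% CI half-width 0.22 m/s), 66% with 8 (0.16), 75% with 10 (0.15) and 81% with 12 (0.13).* In that case also delete the claim that two years of recruitment will power the study.
3. If 245 is kept, show the calculation with every input, including the test and any allowance.
4. State that this contrast is not the comparison in objective 2.3, which will be estimation only among about 12 SOS patients.

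**Cost.** If 80 stands, protocol wording only and no extra patients. The stated power may be less favourable, and recruitment at CMH alone may need longer than two years.

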### 3.0 Background

3.1 Hepatic sinusoidal obstructive syndrome (SOS) is a complication of blood and marrow transplant (BMT) that is associated with high morbidity and mortality. 57,000 patients in the United States and Europe undergo BMT annually (1, 2), and SOS affects up to 15% of these patients (3). SOS pathogenesis is thought to be caused by damage to the hepatic venous endothelium due to the preparative regimen used before BMT. This damage results in obstruction of blood flow through the liver. Pathology shows collagen deposition in the sinusoids and fibrosis of venous lumens (10). The severity of the disease is correlated to the number and severity of the histological changes. Mild and moderate SOS can resolve with supportive treatment. Severe SOS (30% of SOS) is commonly associated with multi-organ failure and has a mortality rate of 80% despite available prophylaxis and treatment (Table 1) (4).

Table 1. Staging of VOD/SOS	Table 1.	Staging	of VOD/SOS 
-----------------------------	----------	---------	--------------------------

Mild : Resolved without interventions	
Moderate : Requires treatment	
• Bilirubin $> 6 \text{ mg/dl}$	
• AST > 5 times upper limit of normal	
• Weight gain $> 5\%$	
• Ascites	
Severe : Progression to Multi-organ dysfunction syndrome	

 
Respiratory failure (O2 saturation < 90 %)
 
	
Hepato renal syndrome	
• Encephalopathy	

- Severe renal failure ( creatinine > x 2)
- Bilirubin > 20 mg/ dl

SOS is most commonly defined by two clinical criteria: the modified Seattle criteria and the Baltimore criteria (Table 2) (11, 12). The modified Seattle criteria state that at least two of the following criteria must be present within 20 days of BMT: bilirubin  $\geq 2mg/dL$ ; hepatomegaly and/or ascites; and/or weight gain  $\geq 5\%$  above baseline weight (11). Pediatric SOS incidence in BMT is 20% and is higher compared to adults (13-15). Death or multi-organ dysfunction affects 30-60% children who develop SOS (16, 17). The most common definition of severe SOS is retrospective, namely death from SOS-related causes or persistent multi-organ dysfunction at 100 days post BMT. However, the European Society for Blood and Marrow Transplantation has proposed a new prospective SOS grading scheme that will likely become standard of care since it is pediatric patient specific and it is can be performed prospectively and thus can guide treatment (5).

Modified Seattle Criteria	Baltimore Criteria

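### The 245-patient calculation in section 28.1 uses a 5.3% moderate-or-severe SOS rate that fits severe SOS alone, conflicts with its own pilot, and is not reconciled with the planned 80

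*Protocol*

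**What the plan says.** Section 28.1 takes its effect size from preliminary data, with velocities in m/s. For the comparison group it reports that "patients with no SOS or mild SOS have an average increase in velocity over baseline of 0.056 m/s at day +5 with (SD of 0.22"). The case group is described as "Our four patients with moderate and severe SOS who received defibrotide", and it "had an average increase in velocity over baseline of 0.25 m/s at day +5 (SD 0.185 m/s"). From these inputs it concludes that "we would need 245 patients (13 with moderate or severe SOS and 232 with no SOS or mild SOS"). The stated target is 80% power at alpha 0.05. It does not name the test, say whether it is one- or two-sided, or explain the 13:232 split.

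Section 3.3 gives the expected yield of this study: "80 additional patients, 12 of which will likely develop SOS (including four with severe SOS"). It describes the pilot thus: "Our study enrolled 25 high-risk BMT patients over 18 months (five with SOS and two with severe SOS"). Section 3.1 states "Severe SOS (30% of SOS" cases) and a pediatric SOS incidence of 20%. Its Table 1 lists moderate SOS as a stage of its own, between mild and severe.

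The planned enrolment is 80 in sections 1.0, 13.1 and 29.1. Section 29.2 names one recruiting site, whereas section 28.1 counts on other sites to reach its target.

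**The concern.** The calculation compares moderate or severe SOS with no or mild SOS, so its case rate should cover both stages. The rate used, 5.3%, is about what the protocol expects for severe disease alone. The mean and SD, however, come from a mixed moderate and severe group that made up 16% of the pilot.

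When one group is this small, its size dominates the standard error, so the assumed case rate largely sets the total N. A reader of section 28.1 would conclude that 80 patients are about a third of what is needed (80/245 = 33%). A reader of section 3.3 together with the pilot could conclude that 80 is roughly enough. The protocol gives no means of choosing between the two, and the study enrols children with no prospect of direct benefit (sections 17.2 and 18.1).

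**Working it through.** **Inputs.** Section 28.1 gives a difference of 0.25 − 0.056 = 0.194 m/s, SDs of 0.185 (cases) and 0.22 (others), alpha 0.05 and power 80%. Two-sided testing is my assumption. I also assume that the four cases in 28.1 belong to the 25-patient pilot of section 3.3.

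**1. Case rates in the protocol**

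- Section 28.1, moderate or severe: 13/245 = 5.3%
- Section 3.3, all SOS: 12/80 = 15%
- Section 3.3, severe only: 4/80 = 5.0%
- Section 3.1, severe only: 0.30 × 15% = 4.5%; 0.30 × 20% = 6%
- Pilot, moderate or severe: 4/25 = 16%, or 4 of the 5 SOS cases
- Pilot share applied to the planned SOS rate (my assumption): 15% × 4/5 = 12%, or 9.6 cases in 80

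**2. The plan's own figure, 13 versus 232.** Power comes from the noncentral t distribution with noncentrality 0.194/SE.

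- Welch: SE = √(0.185²/13 + 0.22²/232) = 0.0533; noncentrality 3.64; about 14 df; power 92%.
- Pooled: SD = √[(12 × 0.185² + 231 × 0.22²)/243] = 0.218; SE = 0.218 × √(1/13 + 1/232) = 0.0622; noncentrality 3.12; 243 df; power 87%.
- Pooled with a common SD of 0.22: power 87%.

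The stated 80% is therefore not reproduced. Only inputs that the protocol does not state come close. Welch with SD 0.22 in both groups gives 81.7% (80% at N = 236), and a pooled test at two-sided alpha 0.025 gives 80.5%.

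**3. Total N for 80% power, by case rate**

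| Moderate-or-severe rate | Welch | Pooled | Common SD 0.22 |
|---|---|---|---|
| 5.3% (section 28.1) | 180 | 200 | 203 |
| 6% | 160 | 179 | 181 |
| 8% | 122 | 137 | 140 |
| 10% | 99 | 112 | 115 |
| 12% | 84 | 95 | 98 |
| 16% (pilot) | 65 | 74 | 78 |

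At 5.3% the surplus over the need is already 245 − 203 = 42 to 245 − 180 = 65 patients. That part comes from the calculation and not from the case rate.

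**4. Power at the planned 80**

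| Cases vs others | Welch | Pooled | Common SD 0.22 |
|---|---|---|---|
| 4 vs 76 (rate of 28.1: 80 × 13/245 = 4.2) | 32% | 40% | 40% |
| 6 vs 74 | 54% | 54% | 54% |
| 10 vs 70 | 80% | 75% | 73% |
| 12 vs 68 (every expected SOS case) | 86% | 81% | 79% |

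**The case against.** The protocol states no planning rate for moderate SOS, and section 3.1 does not divide the non-severe cases into mild and moderate. The 12% and 16% rest on five pilot SOS cases. The exact 95% interval for 4/25 is about 4.5% to 36%, which includes 5.3%; for 4/5 it is 28% to 99.5%. Section 3.3 also calls the pilot patients high-risk, while section 11.1 admits anyone aged 1 month through 21 years having myeloablative conditioning, so a rate below the pilot's is plausible. All of this stands. It rules out calling 5.3% impossible, but it does not explain why 28.1 used a rate that fits only part of the group it names.

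Three stronger readings are tempting, and the documents do not support them.

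- **That 245 is far too large and 80 is adequate.** This needs a moderate SOS rate that the protocol does not give. With 4 to 6 cases, power at 80 is only 32% to 54%.
- **That the calculation leaves almost no room for moderate cases.** At 4/80, 245 patients give 12.25 severe cases, or 0.75 fewer than 13. At 0.30 × 15% they give 11.0, which leaves 2. The remainder turns on rounding 3.6 expected severe cases in 80 (80 × 4.5%) up to four.
- **That the case rate explains the whole excess.** Step 2 of the working shows a separate calculation problem.

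The stakes are also limited. The primary objective is the timing of testing, and objective 2.3 compares groups of SOS patients, so the contrast sized in 28.1 is neither of these exactly. It is, however, the only power statement in the protocol.

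**Conclusion.** The point holds as an inconsistency in the case rate and in the sample size derived from it. Section 28.1 gives the combined moderate-and-severe group a 5.3% rate, which is about the severe-only rate of 4.5% to 6%, while the group that supplied its mean and SD was 16% of the pilot. With the printed difference and SDs and a two-sided t-based test at 0.05, 245 exceeds what 80% power needs at every rate examined from 5.3% upward, from 180–203 at 5.3% down to 65–78 at 16%. The size of the excess cannot be fixed from the protocol, because the moderate rate is unstated and the only evidence for it is a handful of pilot cases. At the planned 80, power for this contrast runs from about 32% with 4 cases to about 86% with 12. The protocol therefore shows neither that 245 are needed nor that 80 are enough.

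**What to change.** In section 28.1:

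- State the moderate-or-severe rate and its source, so that it agrees with section 3.3 (12 SOS cases in 80, four of them severe). Name the test and whether it is one- or two-sided.
- Replace the 245 requirement with the power at the planned 80 over a range of cases: about 32–40% with 4, 54% with 6, 73–80% with 10 and 79–86% with 12. Say that the moderate share rests on five pilot SOS cases. No single point of that range should be printed as the study's power.
- If 13 was meant to be severe cases only, relabel the group and take the mean and SD from the severe pilot patients. There were two, so those estimates would be very imprecise.
- Reconcile 245 and the reliance on other sites with the study-wide 80 and the single recruiting site in sections 29.1 and 29.2.

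The cost is one recalculation and some wording, with no added patients or procedures. The downside is that the stated power becomes a wide range that may lie well below 80%.

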# **10.0 Study Timelines**

10.1 Describe:

- An individual's participation in the study will be during their inpatient stay for their BMT. Once the patient is discharged or Day +100 after BMT is reached, whichever comes first, subject will no longer be in the study.
- July 1, 2018 through June 30, 2020
- June 30, 2021

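### Accrual in 28.1 leans on other sites, but only CMH recruits: its roughly 80 transplants in two years give 48 patients at the stated 60% floor and reach 80 only at 100% enrolment

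*Protocol*

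**What the plan says.** - **Accrual (Protocol 28.1).** "We perform approximately 40 HSCT transplants at CMH every year and in combination with the other sites, we anticipate an enrollment rate of >60" per cent. The rate is a lower bound and is given for CMH together with other sites.
- **Recruitment period (28.1).** "We anticipate needing two years to recruit enough subjects to appropriately power the study". Section 10.1 gives the dates as "July 1, 2018 through June 30, 2020", and 11.1 repeats them.
- **Target.** Section 13.1: "We anticipate enrolling 80 subjects". Sections 1.0, 3.3 and 29.1 also give 80. Section 3.3 expects 12 SOS cases, four of them severe.
- **Recruiting sites (29.2).** "CMH will be the only site recruiting subjects". On the second institution: "The University of Washington – Seattle's involvement is to provide imaging consulting". Sections 1.0 and 6.1 call the study single-site.
- **Eligibility (11.1).** Myeloablative conditioning and age 1 month through 21 years, with further exclusions. The share of the 40 yearly transplants that qualifies is not given.

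**The concern.** The only accrual justification in the protocol counts on sites that, by 29.2, recruit nobody. Without them, the target equals the whole expected CMH transplant volume in the window, with no allowance for ineligibility or refusal.

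If recruitment closes on the stated date, the study is likely to end below 80. The SOS and severe-SOS counts would then fall below those in 3.3. Those counts are already small, and the comparison by treatment need (2.3 and 4.3) depends on them.

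**Working it through.** **Inputs.** 40 transplants a year, an enrolment rate above 60% and two years (28.1); one recruiting site (29.2); target 80 (1.0, 3.3, 13.1, 29.1); SOS incidence 15% (12/80 in 3.3) or 20% (paediatric figure in 3.1, and 5/25 in the preliminary study in 3.3); severe SOS 5% (4/80 in 3.3).

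**1. Can 80 be reproduced?** Expected accrual = transplants per year x years x enrolment rate. Transplants in the window: 40 x 2 = 80.

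| Enrolment rate | Patients in 2 years | Years to reach 80 |
|---|---|---|
| 60% | 48 | 80/24 = 3.3 |
| 70% | 56 | 80/28 = 2.9 |
| 80% | 64 | 80/32 = 2.5 |
| 90% | 72 | 80/36 = 2.2 |
| 100% | 80 | 80/40 = 2.0 |

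Only 100% returns 80. At the floor the shortfall is 80 - 48 = 32 patients (40%). At 60%, 80 patients in two years would need 80/(2 x 0.60) = about 67 transplants a year. From July 1, 2018, 3.3 years runs to about the end of October 2021, past both June 30, 2020 and the later date of June 30, 2021 listed in 10.1.

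**2. Expected cases at 48 patients.**
- SOS at 15%: 48 x 0.15 = 7.2. At 20%: 48 x 0.20 = 9.6.
- Severe SOS at 5%: 48 x 0.05 = 2.4.
- Stated for 80 patients: 12 SOS and 4 severe.

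**3. Power for the 28.1 contrast.** Difference 0.25 - 0.056 = 0.194 m/s; SDs 0.22 m/s (none or mild) and 0.185 m/s (moderate or severe); two-sided alpha 0.05; pooled t test. The noncentrality is 0.194 / [s x sqrt(1/n1 + 1/n0)], where s is the pooled SD (about 0.215 to 0.219) and n1 is the number with moderate or severe SOS. The share with moderate or severe SOS is 13/245 = 5.3% from 28.1. The upper value, 4/25 = 16%, assumes that the four defibrotide-treated patients in 28.1 come from the 25-patient preliminary study.

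The protocol's own case first: 13 and 232 patients give about 87%, against the stated 80%. On this method the stated 245 therefore carries somewhat more power than claimed.

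| N | Share 5.3% | Share 16% |
|---|---|---|
| 48 | n1 = 2.5, power 27% | n1 = 7.7, power 61% |
| 80 | n1 = 4.2, power 42% | n1 = 12.8, power 83% |

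Going from 80 to 48 patients costs about 15 percentage points at the low share (42% to 27%) and 22 at the high share (83% to 61%). At the low share, 80 patients already fall well short of 80% power. That part comes from planning 80 where 28.1 says 245 are needed, not from accrual.

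**The case against.** **The 60% is a floor, and it is not a CMH rate.** This stands. The protocol gives a rate above 60% for combined sites, and nowhere claims that 40 x 2 x 60% makes 80. A reader might infer that CMH will enrol 48, or that the protocol made a multiplication error. The documents support neither. They support a range of 48 to 80, and a contradiction between 28.1 and 29.2 about who recruits. The conclusion survives because any rate below 100% misses 80 in two years.

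**The sentence may be left over from a multi-site plan.** It follows directly after the 245-patient requirement, so this is plausible. It is still current text and the only accrual argument given, so it needs correcting.

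**The yearly volume is approximate.** True, but at the 60% floor it would have to be about 67 rather than 40.

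**The 12 and 4 cases follow from having 80 patients, not from how long they take to recruit.** This also stands. If enrolment is extended until 80 are reached, those counts do not change. They fall only if the study closes on the stated date.

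**Low power is mainly a matter of 80 versus 245.** This stands in part. A reader might attribute the 27% to accrual alone, but the figures at 80 patients show otherwise.

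**Conclusion.** The accrual statement is wrong as written. Section 28.1 relies on other recruiting sites and 29.2 excludes them. On CMH volume alone, the stated two years yield 48 patients at the 60% floor and 80 only with every transplant patient eligible and consenting. At 48 patients, about 7 to 10 SOS cases and 2.4 severe cases are expected instead of 12 and 4.

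This rests on three assumptions: 40 transplants a year holds; the 60% floor, given for combined sites, can be applied to CMH; and all 40 are potentially eligible. If some of the 40 fall outside the age or conditioning criteria and the rate applies to eligible patients only, the yield is lower still, by an amount the protocol does not allow one to compute. The upper power figures also rest on the assumed 16% share.

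The defect concerns feasibility and the stated size. It does not change the definition of any endpoint or analysis.

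**What to change.** 1. In 28.1, delete the clause that counts on other sites, and state the number of eligible CMH patients per year and the CMH-only enrolment rate.
2. Then choose one of two routes:
   - Keep 80 and restate the enrolment period in 10.1, 11.1 and 28.1: up to about 3.3 years at the 60% floor, shorter if a higher rate can be justified.
   - Keep two years and restate the expected number as a range from about 48, with its SOS and severe-SOS counts and precision, in 1.0, 3.3, 13.1, 28.1 and 29.1.
3. Under either route, reconcile the 28.1 wording that two years will recruit enough subjects to power the study with the number kept. The same section says 245 are needed for its contrast, which neither 48 nor 80 meets.

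The cost is a text amendment, plus acceptance of either a longer study or a smaller one with less precision. No procedure or endpoint changes.
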